5.3 Informed Consent Procedures

Database Aim 1: Informed consent will not be obtained from the study subjects, as this would not be feasible for reasons of resources and logistics. As per standard practice, we are requesting a waiver of HIPAA authorization and waiver of informed consent since this is a database study and sample will be recruited from the VA administrative data.

Survey Aim 2 and Qualitative Aim 3: For survey aim 2 (both pilot phase and national survey deployment) and qualitative aim 3 recruitment procedures, we will request a Waiver of HIPAA Authorization and an alteration of the Informed Consent process. As noted in VHA Handbook 1200.05, Appendix C, researchers may petition the IRB for a waiver of informed consent when:

- (a) The research involves no more than minimal tangible or intangible risk to the subjects;
- (b) The waiver or alteration will not adversely affect the rights and welfare of the subjects;
- (c) The research could not practicably be carried out without the waiver or alteration; and
- (d) Whenever appropriate, the subjects must be provided with additional pertinent information after participation.

For the survey aim 2 and qualitative aim 3, we will seek a Waiver of Informed Consent Documentation. We are requesting a waiver of written documentation of consent to reduce risk and burden on participants as well as to ensure feasibility of the study, given the national scope of the aims. As part of the informed consent process, we will email and/or mail individuals an Information Statement that describes the study purpose, requirements, risks and benefits, compensation, confidentiality and privacy, who they can contact with questions, and how they can opt out of further contact. On recruitment calls completed by VA research staff, the staff member will review the Information Statement with the Veteran, prompt questions, and answer questions. The text of the Information Sheet will also be available on the survey website. Veterans will also be informed that participation is fully voluntary and that their decision regarding participation will in no way affect their access to services or the quality of care they receive at the VA.

If, during the conversation with the potential participant, the staff member has concerns that the individual does not understand the study or procedures and is perceived to be unable to provide informed consent, the staff member will consult with [name], and upon agreement, either invite the individual to participate or thank the individual for their time and inform the individual that they are not eligible for the study. Answering survey and/or interview questions will constitute consent to participate.

All research staff will maintain current trainings, including CITI Human Subject Training, VA Privacy and Information Security Awareness and Rules of Behavior, VA Privacy and HIPAA Training, R&D Scope of work.

5.4 Inclusion/Exclusion Criteria

Inclusion criteria for database aim 1: Aim 1 of the study will consist of all Veterans with documentation of a gender dysphoria/gender identity disorder diagnosis code in the VA or in CC from 1999 to the current year for which VA and CC data is available. We will also request a sample of Veterans without a gender dysphoria/gender identity disorder diagnosis code in VA and/or CC or otherwise not identified as TGD through self-identified gender identity (non-TGD) to compare our TGD cohort on variables such as demographics, health condition, utilization, etc.

Inclusion criteria for survey aim 2: For survey aim 2, we will identify Veterans with a documentation of a gender dysphoria/gender identity disorder diagnoses in the VA or CC in the past 2 years at the time of funding.

Inclusion criteria for qualitative aim 3: From survey aim 2, we will recruit a purposive sample of ~70 trans Vets. We will also recruit ~ 20 LGBTQ+ VCCs.

There are no exclusion criteria for any of the aims to allow participation from the full range of trans Vets.

Rational for Involvement of Vulnerable Populations

We will not exclude VA employees, students, pregnant people, economically and/or educationally disadvantaged persons, or terminally ill patients. These participants will not be specifically targeted for recruitment; if participants happen to fall into these subcategories, it would be coincidental. The aim of the study is to examine the health of transgender Veterans – thus, exclusion criteria are minimal to approximate as generalizable a sample as possible. The study procedures would not be of elevated risk to these subpopulations as compared to the general population.

5.5 Study Evaluations

Database Aim 1. Data obtained from the VA administrative data will include identifiers (e.g., name, postal address, email address, phone number), demographics (e.g., age, sex, region, marital status, enrollment priority), vitals (e.g., weight and height), and some behaviors (e.g., smoking and alcohol misuse data) from health factors data. Participants' medical history, diagnoses, treatments, and health care utilization will also be ascertained for both VA and CC from VA administrative data.

Survey Aim 2. Measures will include demographics, setting of gender-affirming treatment receipt (VA, CC), adverse social determinants of health (e.g., housing instability, unemployment), receipt of gender-affirming treatments (e.g. hormones, psychotherapy), barriers and facilitators to gender-affirming treatment in VA and CC, satisfaction with gender-affirming treatment, desire for gender-affirming treatment, depression, anxiety, suicide, minority stress, health conditions/comorbidities, barriers to VA care, quality of life, and smoking. For the pilot testing of the survey, we will elicit open-ended and close-ended feedback about the survey from Veterans to allow for refinement of the survey prior to national deployment of the survey.

Qualitative Interview. Data will be collected from trans Vet participants and LGBTQ+ VCCs during a 45-60-minute and a 30-45 minute telephone/Microsoft teams-based semi-structured interview. Interview guides will contain open-ended questions and areas to query. We will explore trans Vet experiences with barriers and facilitators impacting their ability and desire to access gender-affirming treatments in VA and CC. We will also query them on whether they have used any services and resources in VA and in the community to mitigate these barriers and suggestions on how gender-affirming treatment access might be improved in VA and CC. In addition, we will ask trans Vets about their awareness of gender-affirming treatment availability and coverage in the VA and differences in experiences in accessing gender-affirming treatments in VA and CC.

We will assess LGBTQ+ VCCs perspectives to understand how barriers and facilitators influence trans Vets gender-affirming treatment access in VA and CC and services and resources used by trans Vets to address these barriers. We will also elicit feedback on strategies to improve gender-affirming treatment access in VA and CC from both trans Vets and LGBTQ+ VCCs. These interview guides will be iteratively refined and revised based on database aim 1 and survey 2 findings (e.g., include questions on VA/CC coordination for GATs primarily received in CC, additional barriers identified from Aim 2, etc.) and as needed to ensure that the questions are understood as intended. Modifications may also be made during initial coding if a theme emerges that requires further exploration.

5.6 Data Analysis

Database aim 1: The data analyst under the supervision of the PI will produce summary statistics (e.g., proportions, means) for gender-affirming receipt in VA and/or CC (VA/CC). We will characterize gender-affirming receipt by: 1) patient characteristics, including demographics (e.g. race), comorbidities (e.g. mental health conditions) commonly reported by trans individuals, utilization of VA care (e.g. primary care), 2) site (e.g. region, rural/urban) and 3) setting (VA/CC). As appropriate, two-sided chi-square test (categorical variables), t-test (continuous variables) or their nonparametric equivalent tests will be used to test for the statistical significance of the associations of these patient and site characteristics with gender-affirming receipt. We will also compare the characteristics of patients receiving gender-affirming treatment through VA vs. CC.

Survey aim 2: Our analytical goal is to identify barriers and facilitators associated with receipt of desired gender-affirming treatments in VA and/or CC. In keeping with this goal, the data analyst under the supervision of the PI, will conduct the following analyses:

Descriptive analyses: We will obtain summary statistics (e.g., proportions, 95% confidence intervals, etc.) of the distribution of each gender-affirming treatment, degree of receipt of desired gender-affirming treatments, barriers, and facilitators of gender-affirming treatment. We will characterize the degree of receipt of desired gender-affirming treatments in VA and/or CC. We will also characterize barriers and facilitators by degree of receipt of desired gender-affirming treatments in VA and/or CC, recognizing that trans Vets who received all desired gender-affirming treatments could encounter barriers in receipt of these gender-affirming treatments and trans Vets who received no desired gender-affirming treatments could encounter facilitators in trying to receive gender-affirming treatments. We will also characterize the degree of receipt of desired gender-affirming treatments, barriers and facilitators by age, race/ethnicity, gender identity (transfeminine, transmasculine, non-binary), and region.

Primary analyses: We will conduct bivariate analysis to assess the unadjusted relation of barriers and facilitators with the dependent variables, receipt and desire of gender-affirming treatments in VA and CC. As appropriate, two-sided chi-square tests (categorical variables) or their equivalent non-parametric tests will be used to test the significance of any group differences. We will obtain odds ratios (ORs) and 95% confidence intervals (CI) from separate multivariable logistic regression models, to assess associations between barriers and facilitators for the dependent variables. A multinomial logistic regression model will be used to evaluate associations of barriers and facilitators with the ordinal dependent variable: degree of receipt of desired gender-affirming treatments. These models will adjust for covariates, such as age, race/ethnicity and gender identity. Further, depending on the distribution of respondents across sites, we will examine the distributions of the independent and dependent variables as well as the respondents' characteristics across sites. If there is substantial variation across sites and there are adequate number of respondents (at least 5) in each site, we will adjust for clustering of respondents within sites in the analyses. We will combine sites with small sample sizes into a single cluster for the analyses.

Secondary analyses: To assess interrelationships between barriers, we will examine the overlap of barriers by ascertaining the proportion of trans Vets with various combinations of barriers. To examine this overlap, we will create two variables: 1) a categorical variable, indicating combinations of different barriers (e.g., housing instability only, housing instability and employment, housing instability, unemployment and need to travel for gender-affirming treatments, etc.); 2) number of barriers. We will also explore the effects of these variables in models described in the primary analyses.

Missing data: In a cross-sectional survey, we expect non-response to the entire survey (unit non-response) or to certain questions in the survey (item non-response). We will try to reduce unit non-response by sending two automated email reminders to Veterans to complete the survey. If we have $\geq 10\%$ unit non-response, we will examine the distribution of characteristics between respondents and non-respondents on measures (e.g., age, race/ethnicity, comorbidities, etc.) available in VA data. If necessary, we will create a weight as the inverse of the probability of response from a logistic regression model that predicts response and include these measures as independent variables. These weights will be used in all analyses to reduce bias due to unit non-response. To mitigate item non-response, we will use validated measures, improve the clarity of questions, and use survey branching logic to reduce response burden. Our primary analysis will assume that data are missing completely at random (MCAR) and include only subjects with complete information or computable variables. For items that have $\geq 10\%$ of missing data, we will examine patterns and predictors of missingness and conduct a sensitivity analysis by

imputing the values under the assumptions of missing at random conditional on the observed data. Comparing results from these analyses to that under the MCAR assumption will allow us to assess the amount of bias due to missing data. We will then adjust final models by including predictors of missingness accordingly.

All analyses will be conducted in SAS (SAS, Cary, NC) on complete data. Our tests of significance will be adjusted for multiple testing using the Benjamini-Hochberg procedure to control for the False Discovery Rate.

Qualitative aim 3. We will use a directed content analysis approach. The initial codebook will include a priori codes based on elements of the conceptual model. The qualitative team will come to consensus on codebook definitions in an iterative fashion, adding emergent codes as needed based on newly identified themes and patterns present in the data. To ensure coding consistency, 20% of transcripts will be double-coded and the team will meet periodically during the coding process to resolve any discrepancies through consensus discussion. The resulting coded data will be analyzed to determine domains related to barriers and facilitators around gender-affirming treatment access and desire. Analysis will employ established qualitative techniques, including the constant comparative method, which identifies key themes and concepts from the data to generate meaningful categorization. From the resulting domains, we will develop case studies to further describe the influence barriers and facilitator experiences may have on desire and receipt for trans Vets gender-affirming treatment. Case studies will also note the differences in these barriers to gender-affirming treatment access in VA vs. Summaries of interview findings with both trans Vets and VCCs will be integrated with the survey Aim 2 findings to inform the development of patient-centered strategies.

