5.0 Study Procedures

5.1 Study Design

This is an observational multi-method cross-sectional study with transgender Veterans that will identify barriers and facilitators associated with GAT receipt among trans Vets who desire GATs. We will also identify patient-centered strategies to address barriers and enhance facilitators to improve GAT access. The proposed study will use a mixed-methods design, with three aims. We begin with obtaining national VA data to provide a foundational lay of the land on the GATs received by trans Vets in VA and/or CC (database Aim 1). Next, using a national cross-sectional survey, we will identify barriers and facilitators associated with receipt of desired GATs in VA and CC (survey Aim 2). Finally, by interviewing trans Vets and LGBTQ+ VCCs, we

will understand experiences and perspectives on GAT access in VA and CC, and how to improve this access in VA and CC (qualitative Aim 3).

Database Aim 1: We will expand our VA cohort of 9,608 trans Vets (IIR 17-238) from 2006-18 to the data available at the time of funding. We will add CC data to determine the types of GATs received by trans Vets in VA and/or CC. Aim 1 of the study will consist of all Veterans with documentation of a gender dysphoria (GD) diagnosis code in the VA or in CC from 1999 to the current year for which VA and CC data is available.

Survey Aim 2: We will survey a national sample of up to 1,500 trans Vets with a documentation of a gender dysphoria (GD) diagnoses identified from Aim 1 in the VA or CC in the past 2 years at the time of funding. Among trans Vets who desire GATs, we will determine barriers, and facilitators associated with desired GAT receipt. Among trans Vets who did not desire GATs, we will determine reasons for not wanting GATs. Veterans will be invited by postal mail, email, and phone to participate in a single survey. Similar to our pilot testing recruitment, we will also advertise the survey on VA's LGBTQ+ Health Office website and we will work on recruitment with LGBTQ+ Veteran Care Coordinators (VCCs). Veterans will be encouraged to complete the survey online but will have the option to complete the survey by phone or mail if desired. Data from the survey will be linked to CDW data (available through VINCI) via a study ID, and the crosswalk file will be stored in a separate secure file and will only be accessible to study team members.

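### Aim 1 tests site characteristics against Veteran-level treatment receipt with no allowance for clustering within VA sites, so those p-values may be too small by an amount the documents do not allow one to fix

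*Combined protocol and SAP*

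**What the plan says.** Section 5.6, Database aim 1, breaks treatment receipt down by patient characteristics and then by "2) site (e.g. region, rural/urban) and 3) setting (VA/CC". For inference it states that "two-sided chi-square test (categorical variables), t-test (continuous variables) or their nonparametric equivalent tests will be used". Their purpose is to "test for the statistical significance of the associations of these patient and site characteristics with gender-affirming receipt", so patient-level and site-level variables are handled by the same procedures. Aim 1 contains no regression model, random effect, clustered variance or site-level comparison. It does not name the unit of analysis and gives no numeric significance level.

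Clustering is addressed elsewhere. Under the primary analyses of Survey aim 2, if sites differ substantially and have enough respondents, "we will adjust for clustering of respondents within sites in the analyses". That rule is conditional and concerns survey respondents only.

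Section 5.5, Study Evaluations, places region among the Veteran's own "demographics (e.g., age, sex, region, marital status, enrollment priority" and similar items, whereas section 5.6 calls it a site variable. The cohort before expansion is 9,608 Veterans (section 5.1: "We will expand our VA cohort of 9,608 trans Vets (IIR 17-238) from 2006-18 to the data available at the time of funding"). The expanded size is not stated.

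**The concern.** A characteristic of a VA site takes one value for every Veteran treated there. If sites also differ in how often treatment is received, for reasons unrelated to region or rurality, Veterans at the same site resemble one another in the outcome. A plain chi-square counts each of them as independent evidence about the site characteristic. The standard error is then too small, and ordinary differences between sites can appear as a significant association with region or rurality.

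The protocol foresees this for the survey but not for the database cohort, where there are more Veterans per site. With 130 sites assumed, up to 1,500 survey respondents is about 1,500/130 = 11.5 per site, against 9,608/130 = 73.9 in Aim 1. The Benjamini-Hochberg adjustment at the end of the survey analysis text does not help, because it takes the p-values as given and cannot repair their standard errors.

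At stake is whether statements about where receipt differs are supported. Section 5.5 says the interview guides will be refined in the light of Aim 1.

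**Working it through.** The plan gives no power calculation, p-value or design effect for Aim 1, so there is no stated figure to reproduce.

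**Inputs**
- From the documents: n = 9,608 Veterans; two-sided tests; region and rural/urban as site variables, both categorical.
- Assumed, because the documents do not say: significance level 0.05; number of sites J = 50 to 170, with 130 as the reference; ICC of receipt between sites 0.001 to 0.10; coefficient of variation (CV) of site size 0 or 0.8.

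**Step 1: variable constant within site.** The mean site size is m = 9,608/J. The design effect is DEFF = 1 + (m(1 + CV²) − 1) × ICC. The actual type I error of a nominal 5% test of a two-category variable is 2 × (1 − Φ(1.96/√DEFF)).

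For J = 130 and CV = 0, m = 73.9. At ICC 0.05, DEFF = 1 + 72.9 × 0.05 = 4.65, and the error is 2 × (1 − Φ(1.96/2.16)) = 36.3%. The table gives all values for J = 130. The last column is the range over J = 50 to 170 and CV 0 to 0.8.

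| ICC | DEFF (CV 0) | Type I error (CV 0) | Type I error (CV 0.8) | Range over J and CV |
|---|---|---|---|---|
| 0.001 | 1.07 | 5.8% | 6.4% | 5.6–8.7% |
| 0.01 | 1.73 | 13.6% | 18.7% | 11.6–33.5% |
| 0.02 | 2.46 | 21.1% | 28.8% | 17.7–46.8% |
| 0.05 | 4.65 | 36.3% | 45.9% | 31–63% |
| 0.10 | 8.29 | 49.6% | 58.7% | 44–73% |

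**Step 2: ICC needed to double the error.** Type I error reaches 10% when DEFF = (1.96/1.645)² = 1.42, that is, at ICC = 0.42/(m − 1). With equal site sizes this is 0.0022 at J = 50, 0.0058 at J = 130 and 0.0076 at J = 170.

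**Step 3: more than two categories.** If region has four levels (assumed), the error is P(χ²₃ > 7.81/DEFF). At J = 130 with equal sizes it is 6.3%, 21.1% and 64.1% at ICC 0.001, 0.01 and 0.05.

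**Step 4: variable that varies within site.** The inflation is then roughly DEFF = 1 + (m − 1) × ICC(outcome) × ICC(exposure). With J = 130 and an assumed exposure ICC of 0.2:
- Outcome ICC 0.05: DEFF = 1 + 72.9 × 0.05 × 0.2 = 1.73, and the error is about 14%, not 36%.
- Outcome ICC 0.02: DEFF = 1 + 72.9 × 0.02 × 0.2 = 1.29, and the error is about 8%, not 21%.

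**Step 5: simulation.** This used beta-binomial outcomes, 130 sites, 30% of sites rural and 50% receipt (all assumed), with 4,000 runs per setting. With equal site sizes the unclustered test rejected a true null in 5.9%, 13.6%, 21.2%, 37.0% and 50.3% of runs at the five ICCs in the table, in agreement with the formula. With a site-clustered variance, rejection was 4.8–5.5% with equal sizes and 5.4–6.5% with CV 0.8, for ICCs from 0 to 0.10.

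**The case against.** A reader might infer that the Aim 1 p-values are far too small and that the number of Veterans simply replaces the number of sites. The documents do not support that, for these reasons:

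- **The size is unknown.** With neither ICC nor number of sites given, the result runs from nearly harmless (about 6% at ICC 0.001) to severe. This stands.
- **The level of the variables is not settled.** Section 5.5 treats region as a patient attribute, and rurality could mean the Veteran's residence. Step 4 shows how much that can reduce the inflation. This stands as a limit on size, but section 5.6 itself files both variables under site, so the ambiguity also needs correcting.
- **Veteran-level testing is an inference.** It is the natural reading, because receipt is recorded per Veteran, but the text does not say so. The t-test is beside the point for the two examples named, which are categorical.
- **Aim 1 is descriptive and takes every Veteran with the diagnosis code.** The proportions are not biased. One may argue that a full cohort needs no clustered error, but the plan chooses to run significance tests. Once it does so to draw conclusions beyond this cohort, the standard error should reflect variation between sites.
- **No decision depends on these p-values.** The example in section 5.5 of how Aim 1 shapes the interview guides concerns coordination between VA and Community Care. Under Qualitative aim 3 in section 5.6, the improvement strategies come from the interviews combined with the survey. This stands and lowers the severity.

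The words in the plan that leave the choice of test open do not answer the point, since every test listed assumes independence.

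**Conclusion.** The point holds in a limited form. Aim 1 names tests that assume independence for variables it classes as site characteristics, and provides nothing for clustering within sites, although the survey analysis does. If receipt varies between sites, p-values for variables constant within site will be too small. An ICC of about 0.002 to 0.008 is enough to double the error of a nominal 5% test, given 9,608 Veterans and 50 to 170 equal-sized sites. A larger expanded cohort at the same sites would raise the design effect.

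The true size cannot be determined from the documents, and it is smaller if region or rurality varies within site. Only standard errors and p-values are affected. Severity is moderate.

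**What to change.** In section 5.6, Database aim 1:

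1. State whether region and rural/urban describe the VA site or the Veteran's residence, and bring section 5.5 into line.
2. Assign each Veteran to one VA site by a written rule, for example the site with most visits. Include a rule for Veterans diagnosed only in Community Care and for those who change site, since the cohort runs from 1999 onward and covers both sources.
3. For these variables, replace the plain chi-square with a Rao-Scott chi-square or a logistic model with site as the cluster (SAS SURVEYFREQ or SURVEYLOGISTIC).
4. Report the number of sites and the ICC of receipt, so that readers can judge the size of the effect.

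The plan already uses SAS, so the change of procedure is small. The assignment rule is the larger part of the work. The price is wider intervals for site characteristics and a little extra programming. The descriptive tables need no change.
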